## 1.0 Study Summary

Study Title	An Open-Label, Single- and Multi-Dose Study to Evaluate the Relationship between the Pharmacokinetics, Pharmacodynamics, and Clinical Outcomes of Atomoxetine in CYP2D6 Extensive, Intermediate, and Poor Metabolizers in Children with Attention Deficit/Hyperactivity Disorder
Study Design	This is a non-randomized, un-blinded, exposure escalation efficacy trial of the effects of atomoxetine in children with attention deficit/hyperactivity disorder (ADHD).
Primary Objective	
 
1. To investigate the effect of genetic variability on the pharmacodynamics of ATX by evaluating biomarkers of inhibition of the drug target, the norepinephrine re-uptake transporter, following ATX exposure control.
 
2. To explore how changes in pharmacodynamic markers correspond to clinical response to medication.
 

Secondary Objective(s)	
 
1. To establish the relationship between ATX systemic exposure, inhibition of the norepinephrine uptake transporter, and therapeutic response
 
2. To determine global baseline patient characteristics differences between ATX responders and non-responders.
 
3. To explore how baseline oral microbiome make-up influences clinical outcomes and to describe changes in the oral microbiome with ATX therapy.
 
4. To refine the iGO-PK ATX dosing algorithm.
 
5. To evaluate comprehension of the study procedures by study participants and their families when an illustrated study booklet is supplied with a consent form.
 
6. To validate a urinary CYP2D6 phenotype biomarker.
 

Research Intervention(s)/ Investigational Agent(s)	Atomoxetine – a norepinephrine reuptake transporter inhibitor which is FDA approved for the treatment of ADHD in children. iGO-PK dosing algorithm – a dosing algorithm to normalize atomoxetine exposure regardless of CYP2D6 genotype.

SHORT TITLE: ATX-PBPK-PD-Clinical Outcomes (U54)

IND/IDE #	NA
Study Population	Children, both males and females between the ages of 6-18 with ADHD or a high likelihood of having ADHD, electing to receive care at Children's Mercy Hospital and Clinics and children enrolling in the CMH&C ADHD Summer Treatment Program (STP).
Sample Size	Target enrollment of 160 research participants, in anticipation of 120 participants completing the research study.
Study Duration for Individual Participants	6-8 months
Study Specific Abbreviations/ Definitions	
 
1. ADHD = attention deficit/hyperactivity disorder
 
2. ATX = atomoxetine
 
3. DHPG = dihydroxyphenol glycol
 
4. iGO-PK = individualized genetic and ontogeny pharmacokinetic prediction
 
5. PK = pharmacokinetic
 
6. PD = pharmacodynamic
 
7. Research Visit 1 = RV1
 
8. Research Visit 2 = RV2, or may referred to as pharmacokinetic study 1 (PK1), or first dose PK
 
9. Research Visit 3 = RV3, or may referred to as pharmacokinetic study 2 (PK2), or steady state PK
 
10. Research Visit 4 = RV4, or may be referred to as pharmacokinetic study 3 (PK3), or end of study PK
 

## 2.0 Objectives

### 2.1 Primary Objectives(s):

- To investigate the effect of genetic variability on the pharmacodynamics of ATX by evaluating biomarkers of inhibition of the drug target, the norepinephrine re-uptake transporter, following ATX exposure control.
- To explore how changes in pharmacodynamic markers correspond to clinical response to medication.

### Secondary Objective(s):

- To establish the relationship between ATX systemic exposure, inhibition of the norepinephrine uptake transporter, and therapeutic response
- To determine global baseline patient characteristics differences between ATX responders and non-responders.
- To explore how baseline oral microbiome make-up influences clinical outcomes and to describe changes in the oral microbiome with ATX therapy.
- To refine the iGO-PK ATX dosing algorithm.
- To evaluate comprehension of the study procedures by study participants and their families when an illustrated study booklet is supplied with a consent form (please see Supplementary Documents, “U54 Study Booklet” and “U54 Study Booklet Information Handout”).
- To validate a urinary CYP2D6 phenotype biomarker.

[figure not shown]
### 2.2 Hypotheses to be Tested:

- Hypothesis 1: Genetic variability in the *SLC6A2* gene is associated with variability in 1) concentration-time curves of DHPG and 2) pupil size changes, when evaluating tonic and phasic data.
- Hypothesis 2: Variability in pharmacodynamics markers, i.e. plasma DHPG and pupil size changes, are associated with clinical response to atomoxetine.
- Hypothesis 3: The atomoxetine response cohorts (i.e. response versus non-response and tolerant versus non-tolerant) will have differing global baseline characteristics, such as age, gender, ethnicity, ADHD subtype, genetic polymorphisms, etc.

### 3.0 Background

[figure not shown]
#### 3.1 Atomoxetine Background and Gaps in Knowledge

Atomoxetine (ATX), Strattera®, is a norepinephrine re-uptake transporter inhibitor that is approved by the Food and Drug Administration (FDA) for the treatment of attention deficit/hyperactivity disorder (ADHD) (Seneca et al., 2006; Michelson et al., 2007). The drug is often considered a second- or third-line agent, due to the perception that the drug does not work very well. In fact, in a review of studies submitted to the FDA, Newcorn *et al* reported that there appeared to be discrete classes of response to atomoxetine. After 6-9 weeks of treatment, 47% of the patients were considered “responders” based on changes in the rating scales used to measure ADHD symptoms whereas 40% of patients were considered non-responders (Newcorn *et al.*, 2009). Statistically significant ( $p<0.001$ ) differences in scores between responders and non-responders were apparent after the first week of treatment (Fig. 1).

**Fig 1.** Discrete classes of response to ATX based on patterns of temporal change in ADHD-RS in an analysis of pooled data [2].

At the relatively low starting doses of the titration scheme, this suggests that there may be a subgroup of patients who are particularly responsive to ATX. We hypothesize that there could be two reasons for this: 1) variability in drug pharmacokinetics (i.e., inadequate drug concentrations in the blood over time could lead to poor response) and 2) variability in drug pharmacodynamics (i.e. differences at the level of the target of drug action that limit the response to a drug, regardless of concentration of drug present in the blood). The interplay of pharmacokinetics and pharmacodynamics is presented in Figure 2 below:

**Fig 2.** Interplay of Pharmacokinetic and Pharmacodynamics

The *CYP2D6* gene, which encodes for the drug metabolizing enzyme CYP2D6 responsible for the clearance of ATX from the body, is highly polymorphic (Gaedigk et al., 2007; Gaedigk et al., 2010; Gaedigk et al., 2010; Gaedigk, 2013). ATX metabolism by CYP2D6 protein is one of the major routes of clearance (i.e., removal) of this drug. Genetic variability in the *CYP2D6* gene leads to wide inter-individual variability in the activity of the enzyme, ultimately resulting in differing amount of drug in the body (also referred to as “exposure,” and is a component of drug pharmacokinetics). Secondly, the *SLC6A2* gene which encodes for the norepinephrine reuptake transporter, the drug target for ATX, is also subject to genetic variation. Reported genetic variants of *SLC6A2* have been associated with decreased abundance of the transporter (Kim et al., 2006). The consequences of *SLC6A2* genetic variation with regards to ATX clinical response are currently unknown. In the context of distinct “responder” and “non-responder” groups with a population of atomoxetine-treated patients, non-response could be due to definable differences at the level of the drug target (patients unlikely to respond regardless of the ATX concentrations achieved), or simply a consequence of inadequate exposure in a substantial proportion of population. The goal of this study is to address this issue.

### 3.2 Relevant Preliminary Data

In a previous single-dose ATX pharmacokinetic study conducted at the Children’s Mercy Hospital, we investigated the impact of CYP2D6 genetic variability on drug pharmacokinetics as an initial step in better understanding the poor clinical response to the drug (Brown et al., 2016). The results from the single-dose ATX study found that ATX exposures varied greatly between children (30-50 fold) when administered the same weight-adjusted dose (0.5 mg/kg) with the highest concentrations/exposure in participants deficient in CYP2D6 activity (so-called

“poor metabolizers”) and the lowest exposure in participants who had two or more functional copies of the gene, and the highest CYP2D6 activity.

Furthermore, simulations conducted to investigate the concentrations (exposure) achieved with chronic dosing indicated that a majority of patients with at least one functional copy of the CYP2D6 gene were unlikely to achieve the level of exposure associated with clinical response.

A more important implication of these data is that it is impossible to investigate the effect of differences at the level of the drug target on variability in drug response unless we are able to minimize the variability in drug response that is a consequence of the normal variability in exposure when the same dose (0.5 mg/kg) is given to patients who differ in their ability to eliminate the drug. In other words, we need to develop models and systems by which we can individualize the dose of ATX so that every person has the same exposure. The data collected from this single-dose pharmacokinetic study were subsequently used to build a dosing algorithm to determine a dose that would lead to a desired exposure, defined initially as the peak concentration achieved ( $C_{max}$ ) with *a priori* knowledge of a child’s CYP2D6 genetic information, which can be used to predict activity, in addition to other patient characteristics such as weight and obesity status. The process for validation of this model, termed the individualized **G**enetic and **O**ntogenic **P**harmacokinetics algorithm (iGO-PK), is described in the ATX PBPK Model Validation Study (Appendix A). The major strength of this dosing strategy is that it allows us to ensure that drug exposures do not greatly differ in children, and therefore allows us to describe quantitatively how genetic variability at the drug target alone affects ATX pharmacodynamics and clinical outcomes.

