### **3.3 Study Significance**

Prior studies evaluating variability in drug response are confounded by the highly variable ATX exposures between children, even when given the same weight-based dose, and hence are difficult to interpret (e.g., is a patient truly non-responsive to the medication, or is “non-response” simply due to having inadequate concentrations of the medication in the body). In this investigation we propose to individualize ATX dosing in a cohort of children with ADHD to a standardized exposure goal (based on the maximum concentration achieved, or  $C_{max}$ ), initially using a iGO-PK model derived from our original genotype-stratified PK study, and assign responder or non-responder status according to response criteria established *a priori* by the clinical members of the study team.

Subsequent analyses will investigate predictors of response (metabolomics analysis of pretreatment plasma samples; assessment of biomarkers of ATX inhibition of SLC6A2, such as dihydroxyphenylglycol (DHPG) concentrations and pupil diameter and eye-tracking studies; SLC6A2 genotype; pharmacokinetic-pharmacodynamic (PK/PD) analysis of ATX and DHPG data, etc), as well as differences in exposure→response relationships for different DHPG strata or SLC6A2 genotypes. In addition, the dosing algorithms (iGO-

[figure not shown]
PK) will be updated and revised as the body of pharmacokinetic data increases through the duration of the study.

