## 5.0 Study Intervention/Investigational Agent

### 5.1 Description

ATX is a norepinephrine reuptake transporter inhibitor which is approved by the FDA for use in children with ADHD. The medication displays high inter-individual pharmacokinetic variability, which has been associated with *CYP2D6* genotype. An individual's predicted *CYP2D6* phenotype can be estimated from their genotype. This estimation is quantified as a *CYP2D6* activity score (AS). The *CYP2D6* predicted phenotype and the participant's height, weight, habitus, and gender are used to inform the ATX dosing tool, the individualized genetic and ontogeny pharmacokinetic model (iGO-PK). Both the *CYP2D6* genotype-predicted phenotype activity score and iGO-PK are described below. Doses that are expected to result in  $C_{max,ss}$  values of 400 ng/mL, 600 ng/mL, and 800 ng/mL will be calculated for each participant. Study physicians will start with a dosing regimen that is predicted to achieve a  $C_{max,ss}$  of 400 ng/mL and will titrate the dose to reach  $C_{max,ss}$  values of 600 ng/mL or 800 ng/mL according to participant response. Study physicians may choose to titrate slowly to  $C_{max,ss}$  of 400 ng/mL when initiating ATX therapy to avoid side effects.

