#### *iGO-PK Model*

This method was developed using data generated from a previous ATX single-dose PK study conducted at Children's Mercy Hospital (Brown et al., 2016). This model stratifies participants into two distinct populations: individuals who are CYP2D6 PM and those who non-PMs, i.e. IM, EM1, EM2, and UM (read above for more details on *CYP2D6* genotype and phenotype prediction). With the new changes to *CYP2D6* genotype-to-

phenotype interpretation and study design, the only major change is that children with two reduced function alleles will be modeled as an IM. Analysis of the previous PK study found that in non-PM participants, the dose-exposure relationship was best described using a two-compartment model with first order absorption and first order clearance. In PM participants, dose-exposure was best described using a one compartment model with first order absorption, first order clearance, and a secondary peaking component. Additionally, lean body weight (LBW) and obesity status (positive or negative) variables were found to significantly impact variability in ATX exposure in both models.

Retrograde extrapolation of an initial dose of ATX for PK Study 1 will be determined by setting the desired  $C_{max}$  goal at steady-state ( $C_{max,ss}$ ) to 400 ng/mL, and incorporating patient specific parameters CYP2D6 AS, LBW, and obesity status. The actual dose dispensed will be as close as possible to the model generated dose, given the available atomoxetine capsule formulations. Additionally, we will also consider the most convenient combination of capsules for a child to take and how a prescriber would dose this medication in a naturalistic setting. During the course of the study, we will also be monitoring clinical response and toxicity. The exposure ( $C_{max,ss}$ ) may be titrated down to below 400 ng/mL to reduce toxicity or up to 800 ng/mL to increase response as tolerated.

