Variables that will be included in this analysis are data collected at the patient's initial clinic visit: DHPG, *SLC6A2* genotype, ADHD subtype, ADHD severity, co-morbid anxiety or oppositional defiant disorder, age, and gender. Predictive power of classification models will be assessed by computing the area under the receiver operating characteristic curve and/or by k-fold cross-validation. Two-sample t-tests or non-parametric alternatives will be utilized to test for group differences in percent decrease in DHPG and a differences in proportions test will be used to assess the association between response and *SLC6A2* genotype. In addition, global metabolomic analyses will be conducted to determine whether non-responders and responders are intrinsically different in their biochemical make-up. This will further understanding of how differences in

response phenotype could be a result of different biological pathway involvement in ADHD. Digital maps will be constructed for partial least square-discriminant analysis (PLS-DA) models with prior knowledge of which volunteers were categorized as responders and non-responders. The variable influence on the projection (VIP) parameter will be used to identify which metabolites (i.e. pathways) are the most predictive of differentiating between the responder and non-responder populations. Analyses will also be conducted to determine mechanistic reasons for why certain individuals are non-responders or responders. Changes in pharmacodynamic endpoints will be compared between responders and non-responders. Specifically pharmacodynamic parameters such as  $I_{max}$ ,  $IC_{50}$ , differences in pupil diameter changes in localizations and discrimination tasks, and overall change in DHPG will be compared between the two populations using MANOVA and/or appropriate two-sample test.

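### Dosing targets only the predicted steady-state peak, so AUC, trough and first-dose peak still vary with CYP2D6, and the responder comparisons of raw DHPG and pupil change name no term for it

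*Combined protocol and SAP*

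**What the plan says.** - **Target of dosing.** Section 3.2 describes the exposure that the algorithm aims for as "defined initially as the peak concentration achieved", and states that "it allows us to ensure that drug exposures do not greatly differ in children". It infers that the effect of the drug target alone can then be quantified. Section 3.3 repeats the aim to "individualize ATX dosing in a cohort of children with ADHD to a standardized exposure goal", again based on Cmax. No section sets a target for AUC or trough.
- **First dose.** Section 5.1 (iGO-PK Model): "Retrograde extrapolation of an initial dose of ATX for PK Study 1 will be determined by setting the desired" Cmax at steady state, 400 ng/mL. The Research Visit 2 dose therefore comes from a steady-state goal. The target may later move below 400 or "up to 800 ng/mL to increase response as tolerated".
- **Responder analyses.** Section 20.1 (Clinical Outcomes) lists DHPG and SLC6A2 genotype, then "ADHD subtype, ADHD severity, co-morbid anxiety or oppositional defiant disorder, age, and gender", all from the initial clinic visit. Percent DHPG decrease is compared by two-sample test. Imax, IC50, pupil change and overall DHPG change are compared by MANOVA or two-sample tests. Section 20.2 repeats the two-sample approach. None names CYP2D6 or exposure. The only confounder named for correlating PD change with response is adherence.
- **SLC6A2 groups.** PD parameters are compared by ANOVA. The ANCOVA that follows covers demographic variables.
- **Where exposure is used.** Section 20.1 models DHPG on plasma concentration, regresses pupil and eye-tracking data on Cmax and AUC0-∞, and relates task performance and heart rate to exposure and Cmax.

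**The concern.** The design rests on removing pharmacokinetic differences, so that what remains reflects the norepinephrine transporter. Matching the peak does not do that. With equal Cmax,ss, a child with slower clearance keeps drug on board for more of the day. Section 3.1 itself frames the pharmacokinetic explanation for non-response as concentrations over time, and section 4.1 describes DHPG suppression as lasting for hours.

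At Research Visit 2 the imbalance reverses. A slow metaboliser accumulates, so a dose chosen for the steady-state peak gives a lower first peak than in a normal metaboliser.

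If longer inhibition raises both the PD change and the chance of response, a responder test of raw DHPG or pupil change can show an association that comes from CYP2D6 rather than from the target. This applies even to children who stay at the 400 ng/mL target, and adjusting for Cmax would not remove it.

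**Working it through.** The plan gives no AUC, trough or first-dose figure under peak matching, so there is nothing of its own to reproduce on this point.

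**Inputs from the documents.** Cmax,ss target 400 ng/mL (5.1); usual dosing once daily, so τ = 24 h (11.1); 96 patients after attrition, 30% responders, one-sided α 0.05, detectable difference 0.6 SD (20.2).

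**Assumed, because the documents do not give them.** Half-life 2.4–5 h (normal), 14–24 h (poor-metaboliser-like) or 6–10 h (intermediate); ka 0.7–3 per h. One compartment with first-order absorption is a simplification: section 5.1 uses two compartments for non-poor metabolisers and a secondary peak for poor metabolisers.

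**Formulas.** With k = ln 2 / t½:
- Steady state: C(t) = A·ka/(ka−k)·[e^(−kt)/(1−e^(−kτ)) − e^(−ka·t)/(1−e^(−ka·τ))], with A chosen so that the maximum is 400.
- AUC over τ = A/k.
- First-dose peak = A·e^(−k·tmax), with tmax = ln(ka/k)/(ka−k).

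**Central case** (4 h against 20 h, ka 2 per h):
- Normal: k = 0.1733, A = 495.8. AUC = 495.8/0.1733 = 2861 ng·h/mL; trough 8.6; first-dose peak 393 ng/mL.
- Slow: k = 0.03466, A = 240.2. AUC = 240.2/0.03466 = 6931 ng·h/mL; trough 188; first-dose peak 224 ng/mL.
- Slow/normal: AUC 2.4, trough 22, first-dose peak 0.57.

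**Range over the assumptions:**
- Poor-metaboliser-like: AUC ratio 1.6 (5 h against 14 h, ka 0.7) to 4.1 (2.4 h against 24 h, ka 3). Trough about 130–230 against 1–26 ng/mL. First-dose peak 0.5–0.7 of normal.
- Intermediate, against normal 3–5 h with ka 1–3: AUC ratio 1.1–2.4, first-dose peak 0.80–0.97. Allowing 2.4 h for the normal child stretches the upper AUC ratio to 2.9.
- Normal child (4 h) dosed every 12 h against slow child (20 h) once daily, ka 2: AUC 6931/5030 = 1.4, trough 188/68 = 2.8.

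**The planned AUC is not comparable across designs.** Section 20.1 (Pharmacokinetics) takes AUC0-τ to 12 or 24 h by study design. In the central case the normal child's AUC to 12 h is 2513, so the planned figures give 6931/2513 = 2.8 where the like-for-like ratio is 2.4.

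**Possible effect on a responder test** (illustration; every input in this step except 96 and 30% is assumed). Let slow metabolisers be 5–15% of children, respond in 40–60% against 30%, and have a PD shift of 0.5–1 SD.
- Upper end: the slow share among responders is 0.15×0.6/(0.15×0.6 + 0.85×0.3) = 0.261. Among non-responders it is 0.15×0.4/(0.15×0.4 + 0.85×0.7) = 0.092. The spurious difference is 0.169 × 1 = 0.17 SD.
- Lower end: (0.066 − 0.043) × 0.5 = 0.01 SD.
- Standard error with 28.8 and 67.2 children: √(1/28.8 + 1/67.2) = 0.223 SD. At 0.17 SD, about 0.76 standard errors, the one-sided 5% false-positive rate becomes 1 − Φ(1.645 − 0.76) ≈ 19%. At 0.01 SD it barely moves.

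**The case against.** The strongest reply is that the plan does handle exposure. DHPG Imax and IC50 come from a model driven by concentration, and pupil, task and heart-rate data are analysed against exposure. CYP2D6 is a named gene for variant analysis of safety, efficacy and toxicity, and exposure–response is a secondary objective. This stands. A reader might infer that the PD analyses ignore exposure altogether; section 20.1 does not support that, and the Clinical Outcomes group comparisons contain no heart-rate comparison. But these analyses describe exposure and effect. They do not adjust the responder comparisons of raw change. The variant panel in 20.2 is tested in the same way as SLC6A2, one comparison at a time.

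A reader might also infer one fixed multiple for AUC and trough. The half-lives are assumptions, intermediate metabolisers differ less, and the once-daily trough gap in poor-metaboliser-like cases is far wider than the AUC gap.

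Nor is the SLC6A2 comparison shown to be biased: that would need an association between SLC6A2 and CYP2D6, and the documents give no evidence of one. There the omitted term mainly costs precision.

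Finally, section 3.2 speaks of exposures not differing greatly, against a 30–50-fold range at equal weight-based dose, and nowhere claims that first-dose peaks match. That is fair. What goes too far is the step to the target alone.

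**Conclusion.** The point holds within limits. Only predicted Cmax,ss is targeted, so AUC, trough and first-dose peak remain linked to CYP2D6. The responder classifier and the responder tests of raw DHPG and pupil change carry no term for this. An unadjusted difference can still show that a marker goes with response, but it cannot assign that difference to the drug target.

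Under the stated half-lives and once-daily dosing, the AUC gap is 1.6–4.1-fold for poor-metaboliser-like children and about 1.1–2.4-fold for intermediate ones. That the gap exists follows from the dosing rule and different clearances; its size rests on the assumed values. The resulting bias depends on the share of slow metabolisers, which the documents do not give. In the illustration it runs from negligible to 0.17 SD, below the 0.6 SD the plan is powered for but enough at the upper end to disturb the error rate.

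**What to change.** 1. Add the baseline CYP2D6 activity score to the predictor list in 20.1, and as a covariate in the group comparisons of raw DHPG and pupil change, by responder status and by SLC6A2 group.
2. As a sensitivity analysis, adjust the Research Visit 2 and 3 PD comparisons for the exposure observed at that visit. Visit 2 is the cleaner of the two, because Visit 3 can follow dose changes. Do not put on-treatment AUC in the classifier: the list is baseline-only, and later AUC partly reflects titration on response.
3. Assess exposure control on a common AUC0-24,ss for all study designs, in place of AUC to 12 or 24 h by design. In once-daily Study Design 2 children, the pre-dose sample at Research Visits 3 and 4 can serve as the 24 h value if the time of the previous dose is recorded.
4. Limit the claim in 3.2 to predicted steady-state peak concentrations.

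No dose, visit or sample changes. Genotype and concentrations are already collected. The cost is one further baseline covariate with 0.30 × 96 ≈ 29 expected responders: counting eight listed predictors, responders per predictor fall from 29/8 = 3.6 to 29/9 = 3.2. The classifier is thin already, so the cross-validation that 20.1 offers as an option matters more. The rest is a small amount of analysis and wording.
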